13. APPENDICES

13.1 Clinical Laboratory Parameters

All hematology and clinical chemistry parameters as well as the listed screening tests will be analyzed at a central laboratory. Urinalysis parameters, assessed by dipsticks, will be analyzed locally using provided kits. Sample for clinical laboratory tests will be collected at times specified in [Table 2 Blood Sampling Times by Parameter for Visit 1—Part A](#).

Hematology

Platelet Count	RBC Indices:	Automated WBC Differential:
RBC Count	MCV	Neutrophils
WBC Count (absolute)	MCH	Lymphocytes
Reticulocyte Count	MCHC	Monocytes
Hemoglobin		Eosinophils
Hematocrit		Basophils

Clinical Chemistry

Urea	Potassium	AST (SGOT)	Total and direct bilirubin
Creatinine	Chloride	ALT (SGPT)	Uric Acid
Glucose	Total CO ₂	GGT	Albumin
Sodium	Calcium	Alkaline phosphatase	Total Protein

Other Parameters

HBsAg (Hepatitis B Surface Antigen);
HCVAb (Hepatitis C antibody)
Pregnancy test (urine)
Fasting serum lipid measurements to include: total cholesterol, HDL, LDL, triglycerides

Urinalysis

pH, glucose, protein, blood and ketones by dipstick provided by sponsor

13.2 Tanner Stages

The Tanner stages, developed by [Marshall and Tanner \(1969\)](#) is a commonly used system to categorize pubertal maturation in terms of sequence, timing and tempo as described below.

Boys - development of external genitalia

- Stage 1: Prepubertal
- Stage 2: Enlargement of scrotum and testes; scrotum skin reddens and changes in texture
- Stage 3: Enlargement of penis (length at first); further growth of testes
- Stage 4: Increased size of penis with growth in breadth and development of glans; testes and scrotum larger, scrotum skin darker
- Stage 5: Adult genitalia

Girls - breast development

- Stage 1: Prepubertal
- Stage 2: Breast bud stage with elevation of breast and papilla; enlargement of areola
- Stage 3: Further enlargement of breast and areola; no separation of their contour
- Stage 4: Areola and papilla form a secondary mound above level of breast
- Stage 5: Mature stage: projection of papilla only, related to recession of areola

Boys and girls - pubic hair

- Stage 1: Prepubertal (can see velus hair similar to abdominal wall)
- Stage 2: Sparse growth of long, slightly pigmented hair, straight or curled, at base of penis or along labia
- Stage 3: Darker, coarser and more curled hair, spreading sparsely over junction of pubes
- Stage 4: Hair adult in type, but covering smaller area than in adult; no spread to medial surface of thighs
- Stage 5: Adult in type and quantity, with horizontal distribution ("feminine")

### 3. LIST OF ABBREVIATIONS

ABBREVIATION	DEFINITION OR DESCRIPTION
°C	Degree Celsius
°F	Degree Fahrenheit
ADaM	CDISC Analysis Dataset Model
AE	Adverse event
ALP	Alkaline phosphatase
ALT	Alanine aminotransferase or SGPT
AST	Aspartate transaminase or SGOT
ATC	Anatomical Therapeutic Chemical
AUC	Area under the Serum Concentration-Time Curve
CDISC	Clinical Data Interchange Standards Consortium
C max	Maximum drug concentration
CPP	Central Precocious Puberty
CSR	Clinical study report
CV	Coefficient of Variation
DD	Day
dL	deciliter
EMA	European Medicines Agency
FDA	Food and Drug Administration
FSH	Follicle Stimulating Hormone
GnRH	Gonadotropin Releasing Hormone
GnRH a	Gonadotropin Releasing Hormone Agonist
ICH	International Conference on Harmonization of Technical Requirements of Pharmaceuticals for Human Use
ICF	Informed Consent Form
kg	Kilogram(s)
LH	Luteinizing Hormone
MedDRA ®	Medical Dictionary for Regulatory Activities
mIU	Milli International Units
mL	Milliliter(s)
mm Hg	Millimeters of Mercury
N	Sample Size
ng	Nanogram

PD	Pharmacodynamic
PE	Physical Examination
pg	Picogram
PK	Pharmacokinetic
PP	Per-protocol [population]
SAP	Statistical analysis plan
SC	Subcutaneous(ly)
SD	Standard deviation
SDTM	Study Data Tabulation Model
TBL	Total bilirubin
TEAE	Treatment-emergent adverse event
T max	Time of maximum (peak) drug concentration
ULRR	Upper limit of the reference range
WHO-Drug	World Health organization

#### 4. BACKGROUND AND PURPOSE

This Statistical Analysis Plan (SAP) describes the planned procedures and analyses for TOLMAR study TOL2581A: *An Open-label, Single Arm, Multicenter Study on the Efficacy, Safety, and Pharmacokinetics of Leuprolide Acetate 45 mg for Injectable Suspension Controlled Release in Subjects with Central (Gonadotropin-Dependent) Precocious Puberty*. This study is a multicenter, open-label, single-arm, adaptive, interventional study to assess efficacy, safety and pharmacokinetics/pharmacodynamics with up to two study phases (Part A and Part B) distinguished by dosing schedule.

This SAP is compliant with the principles set forth in guidance documents by the Food and Drug Administration (FDA), the European Medicines Agency (EMA), the American Statistical Associationi, the Royal Statistical Societyii and the International Conference on Harmonization of Technical Requirements for Registration of Pharmaceuticals for Human Use (ICH): Guidance on Statistical Principles in Clinical Trials (E9)iii.

Additional analyses and modifications to those found in this SAP will be allowed. Any such changes that are added *prior to examination of the data by the statistician* will be listed in a future appendix to this document (i.e., Appendix 4). Procedures in the final version of this SAP and the noted appendix may be referenced as *a priori* in documents describing the safety, efficacy and pharmacokinetics outcomes of TOLMAR Study TOL2581A. Any statistical analyses for Study TOL2581A that fall outside those described in the final version of this SAP and the noted appendix will be designated as “post hoc”.

To ensure that the evaluative data for this study are accurate, edit checks will be described in and implemented according to a Data Management Plan.

This SAP assumes reader familiarity with the Study TOL2581A protocol and any protocol amendments.

## **5. STUDY OBJECTIVES**

### **5.1. Primary Objective**

The primary objective of this study is to determine the effectiveness of leuprolide acetate 45 mg for injectable suspension for the treatment of children with central precocious puberty (CPP).

### **5.2. Secondary Objectives**

The secondary objectives of this study are to:

- Evaluate the safety and tolerability of leuprolide acetate 45 mg for injectable suspension in children with CPP;
- Characterize the burst kinetics of leuprolide acetate 45 mg after the first administration;
- Characterize the pharmacodynamic (PD) relationship of leuprolide serum concentrations to concentrations of serum luteinizing hormone (LH), follicle stimulating hormone (FSH) and testosterone/estradiol;
- Assess percent change from baseline in height and bone age after the first treatment administration;
- Assess growth velocity of height in cm/year after the first treatment administration;
- Assess changes in physical signs of puberty as measured by changes in Tanner stages or in changes or onset of menses; and
- Determine the dosing interval (5 or 6 months) at which leuprolide acetate is able to suppress LH concentration to <4 mIU/mL (after gonadotropin releasing hormone agonist [GnRHa] stimulation test) as data permits.

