7.2 Secondary Objectives

[figure not shown]
- Evaluate the safety and tolerability of leuprolide acetate 45 mg for injectable suspension in children with CPP
- Characterize the burst kinetics of leuprolide acetate 45 mg after the first administration
- Characterize the pharmacodynamic (PD) relationship of leuprolide serum concentrations to concentrations of serum LH, FSH and to testosterone/estradiol
- Assess percent changes in height velocity and bone age progression after the first administration
- Assess changes in physical signs of puberty as measured by changes in Tanner stages or in changes or onset of menses
- Determine the dosing interval (5 or 6 months) at which leuprolide acetate is able to suppress LH concentration to <4 mIU/mL (after GnRHa stimulation test), as data permit

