8.6.1 Screening Visit

Screening assessments will be performed during the 28-day Screening period and prior to the first injection, unless otherwise specified. During screening, the following procedures and evaluations will be performed:

1. Informed consent and assent (if required); may be signed up to 28 days prior to Baseline/Day 0
2. Inclusion/exclusion criteria
3. Demographics
4. Medical History
5. Vital signs – measured prior to any blood draws
6. Prior and concomitant medications
7. Physical Examination-complete
8. Tanner stage
9. Height and weight
10. X-ray of non-dominant hand and wrist
11. Urine for urinalysis, performed using dipstick supplied by Sponsor
NOTE: results must be evaluated before dosing
12. Blood samples for clinical laboratory assessments
 - Hematology and chemistry parameters as per [Appendix 13.1](#)
 - Serum lipids, fasting for ≥ 8 hours (water permitted)
 - Hepatitis B Surface Antigen (HBsAg) and hepatitis C antibody (HCBAb)
13. Blood samples for basal LH, FSH, testosterone/estradiol concentrations PRIOR to the GnRHa stimulation
14. Blood samples for basal leuprolide concentrations PRIOR to the GnRHa stimulation
15. GnRHa stimulation: aqueous leuprolide acetate 20 $\mu\text{g}/\text{kg}$ body weight administered SC
16. Blood samples for LH, FSH, testosterone/estradiol concentrations 30 \pm 5 minutes AFTER the GnRHa stimulation
17. Schedule/confirm next visit

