9.2.2 Efficacy Evaluations

Primary Efficacy Endpoint

- **Part A:** the percentage of subjects with serum LH concentrations < 4 mIU/mL 30 minutes following an abbreviated GnRHa stimulation test at the Month 6 visit
Leuprolide Acetate 45 mg will be considered effective for the treatment of children with CPP if $\geq 80\%$ of subjects exhibit LH suppression < 4 mIU/mL at Month 6
- **Part B Extension:** the percentage of subjects with serum LH concentrations < 4 mIU/mL 30 minutes following an abbreviated GnRHa stimulation test at the Month 21 visit (5 months after the Injection #4 of leuprolide acetate)

Leuprolide acetate 45 mg will be considered effective for the treatment of children with CPP if $\geq 80\%$ of subjects exhibit LH suppression < 4 mIU/mL at the Month 21 visit (5 months after the last of 4 administrations of the study drug)

NOTE: If Part B extension is conducted, the primary efficacy endpoint for Part A will become a secondary efficacy endpoint of Part B.

Secondary Efficacy Endpoint: Parts A & B

- The percentage of subjects with suppressed serum LH concentrations (< 4 mIU/mL) 30 minutes post GnRHa stimulation test at all assessed time points
- Changes in height velocity (growth rate), and bone age advancement will be evaluated relative to chronological age using descriptive statistics from baseline to end of study
- Changes in physical signs of puberty as measured by changes in Tanner stages from baseline to end of study

Exploratory Assessments: Parts A & B

- Bone age progression will be further evaluated using descriptive statistics and figures at all assessed timepoints. Changes in bone age progression will be described for each individual and for the ITT and PP population over the entire treatment period
- Descriptive statistics will be used to describe changes in physical signs of puberty as measured by changes in Tanner stages at each assessed timepoint. Changes in Tanner staging will be described for each individual and for the ITT and PP population over the entire treatment period.
- The percentage of subjects with LH (< 4 mIU/mL), FSH (< 2.5 mIU/mL), estradiol (< 20 pg/mL) or testosterone (< 30 ng/dL) suppression to prepubertal levels and serum leuprolide levels at all assessed timepoints

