### **8.2.2. Secondary Efficacy Endpoints and Assessments**

Serving as secondary endpoints will be the following variables.

- The percentage of subjects with serum LH concentrations < 4 mIU/mL at 30 minutes following an abbreviated GnRHa Stimulation Test for any available measurement other than the measurement constituting the primary outcome variable (see above).
- The percent change from baseline in height at each available post-baseline measurement. Percent change is defined as  $((\text{change from Baseline})/(\text{Baseline})) \times 100$ .
- The growth velocity of height in cm/year at each available post-baseline measurement. Growth velocity is defined for each visit as  $(\text{change from Baseline})/[(\text{number of weeks since Baseline})/52]$ .
- The ratio of bone age at each given measurement point to chronological age at the same measurement points.
- Baseline to end-of-study stage shifts for each Tanner category.
- The percent change from baseline in hormonal concentration (LH, FSH, Testosterone, and Estradiol) at each available post-baseline measurement. Percent change is defined as  $((\text{change from baseline})/(\text{baseline})) \times 100$ .
- The percent change from baseline in systemic leuprolide concentration at each available post-baseline measurement. Percent change is defined as  $((\text{change from baseline})/(\text{baseline})) \times 100$ .

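### The protocol's percent change in height velocity cannot be estimated from the planned data, and neither growth measure in the SAP stands in for it

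*SAP*

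**What the plan says.** **Protocol.** The Synopsis and section 7.2 give the objective as "Assess percent changes in height velocity and bone age progression after the first administration". Section 9.2.2 has a secondary endpoint on how growth alters over the study, under which "height velocity (growth rate), and bone age advancement will be evaluated relative to chronological age using descriptive statistics from baseline to end of study".

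**SAP.** Section 5.2 lists two growth objectives, one after the other: "Assess percent change from baseline in height and bone age after the first treatment administration" and "Assess growth velocity of height in cm/year after the first treatment administration". Section 8.2.2 turns them into two endpoints: "The percent change from baseline in height at each available post-baseline measurement" and "The growth velocity of height in cm/year at each available post-baseline measurement". Velocity is defined as height gained since Baseline divided by years since Baseline (weeks/52). The change log in Appendix 4 shows that the velocity objective and endpoint both came in with version 1.4. No change or percent change in velocity is defined. The SAP relates bone age, but not velocity, to chronological age. Table 5 has a row for height and none for velocity.

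**Heights available before dosing.** Protocol 8.6.1 states: "Screening assessments will be performed during the 28-day Screening period and prior to the first injection". Height is taken then and again before dosing on Day 0 (8.6.2). Medical history (8.4.3) covers illnesses, conditions and procedures, and lists no earlier heights. The study has one arm, and neither document names a growth reference.

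**The concern.** A percent change in velocity needs a reference velocity. For the protocol's wording that means the rate before the first injection, and the plan has no usable estimate of it. Of the SAP's two measures, one is a change in height and not in velocity. The other is a velocity without a change.

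At stake is a secondary efficacy objective of a pivotal study. As planned, the report would hold growth tables that cannot answer the stated question. The percent change in height would be positive for every child who grew, with nothing to say whether that growth was slower than before treatment. An interval analysis devised after the data are seen would have to be labelled post hoc under SAP section 4.

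**Working it through.** The documents give no figure for height or velocity, so there is nothing of theirs to reproduce. The heights and velocities below are illustrative assumptions. The visit weeks, the ±1 mm reading limit (Protocol 8.4.7) and the formulas come from the documents.

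**1. Is there a usable pre-dose velocity?** Two readings, each to ±0.1 cm, give a worst-case error of 0.2 cm in their difference. The velocity error is 0.2/(weeks/52).

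| Gap | Worst-case error (cm/year) |
|---|---|
| 7 days | 0.2/(1/52) = ±10.4 |
| 14 days | 0.2/(2/52) = ±5.2 |
| 28 days (maximum) | 0.2/(4/52) = ±2.6 |
| 24 weeks | 0.2/(24/52) = ±0.43 |
| 48 weeks | 0.2/(48/52) = ±0.22 |

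This counts the reading limit only. The pre-dose gap is too short to serve as a reference.

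**2. The SAP velocity at Baseline.** Both the height gain and the elapsed time are zero, so the formula gives 0/0. It supplies no baseline from which to take a change.

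**3. Do the SAP measures respond to the pre-treatment rate?** Assume a Day 0 height of 125 cm and 6 cm/year on treatment. At Week 48 the gain is 6 × 48/52 = 5.54 cm. Percent change in height is 100 × 5.54/125 = +4.43%, and the SAP velocity is 5.54/(48/52) = 6.0 cm/year. The protocol's quantity is 100 × (6 − pre)/pre:

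| Assumed pre-treatment velocity (cm/year) | Percent change in velocity | SAP percent change in height | SAP velocity (cm/year) |
|---|---|---|---|
| 4 | +50% | +4.43% | 6.0 |
| 6 | 0% | +4.43% | 6.0 |
| 9 | −33% | +4.43% | 6.0 |
| 12 | −50% | +4.43% | 6.0 |

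Both SAP measures stay the same while the protocol's quantity runs from +50% to −50%.

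**4. Does the cumulative velocity show slowing on treatment?** Assume 9 cm/year in Weeks 0–24 and 5 cm/year in Weeks 24–48. The gains are 9 × 24/52 = 4.15 cm and 5 × 24/52 = 2.31 cm. The SAP value is 9.0 at Week 24 and (4.15 + 2.31)/(48/52) = 7.0 at Week 48.
- Change in the SAP value: 100 × (7 − 9)/9 = −22%.
- Change in interval velocity: 100 × (5 − 9)/9 = −44%.

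The slowing is visible but appears half its size.

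**5. Percent change in height.** At Week 48 it is 100 × v × (48/52)/H₀. For starting heights of 100–145 cm and velocities of 3–10 cm/year it runs from 100 × 3 × (48/52)/145 = +1.9% to 100 × 10 × (48/52)/100 = +9.2%, always positive. Starting height can reverse the order of two children: 6 cm/year from 110 cm gives +5.0%, and 7 cm/year from 140 cm gives +4.6%.

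**The case against.** The strongest reply is that the SAP does analyse velocity. A reader who stops at the percent-change bullet might infer that height has replaced velocity altogether. The next bullet, and the matching endpoint in 8.2.2, show otherwise. SAP section 7 also says that time points will be compared by setting their descriptive results side by side, and it plans individual height plots. Velocity at Week 24 can therefore be contrasted with Week 48 under the existing text. That stands, but it does not close the gap: the contrast is between cumulative averages (step 4), and it says nothing about the rate before treatment.

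Three further inferences would go too far.
- A reader might say that no pre-treatment velocity exists. Two pre-dose heights are scheduled; the interval is too short for them to be useful.
- A reader might say that percent change in height cannot tell slow growers from fast ones. With 5 and 10 cm/year and starting heights of 110 and 140 cm, the Week 48 values are 3.3–4.2% and 6.6–8.4%, which do not overlap. The measure blurs velocities that are close together and does not erase large differences.
- A reader might take the first on-treatment interval as a conservative reference. If velocity falls at once from an assumed 10 to 5 cm/year and stays there, the between-interval change is 0% against a true −50%. If growth slows naturally with no drug effect, the change is negative and looks like benefit. The error can go either way.

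It is also fair that the consequence is bounded. Efficacy is claimed on the LH percentage alone (SAP 6.6 and 8.2.1), and the growth results are descriptive.

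**Conclusion.** The plan is wrong as written on this objective. Percent change in height velocity from the pre-treatment rate cannot be estimated: the pre-dose interval is at most 28 days, with up to ±2.6 cm/year of reading error at its longest, and there is no control arm or growth reference. The velocity added in SAP version 1.4 is useful on-treatment information. It is cumulative, however, has no value at Baseline, carries no derived change, and understates slowing during treatment (−22% against −44% in the assumed case). Percent change in height does not measure the objective.

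The mismatch between the documents, the 28-day limit and the 0/0 at Baseline rest on the documents alone. The sizes in steps 3 to 5 rest on assumed heights and velocities. The documents do not support saying that growth velocity goes unanalysed, or that the primary conclusion is affected.

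**What to change.** **In SAP 5.2 and 8.2.2,** add interval velocity: the height difference between two visits divided by the years between them, with its change and percent change from one interval to the next.
- Part A only: Day 0–Week 24 and Week 24–48.
- Part B subjects, who have no Part A Week 48 visit: Day 0–Week 24, then Weeks 24–44, 44–64 and 64–80.

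All these heights are already scheduled. Percent change in height may stay as a descriptive listing, but should not be offered as evidence for this objective.

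**In both documents,** restate the objective as on-treatment growth velocity and its on-treatment change. State that this is not a change from the pre-treatment rate and is not necessarily conservative, because it misses an immediate sustained fall and cannot separate drug effect from natural slowing. Keeping the protocol's present objective would need documented pre-study heights, which neither document plans to collect.

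**Cost.** One derived variable, a wording change in each document, and a more modest stated objective. Interval velocities are also noisier than a 48-week average: worst-case reading error is ±0.43 cm/year over 24 weeks, 0.2/(20/52) = ±0.52 over 20 weeks and 0.2/(16/52) = ±0.65 over 16 weeks, against ±0.22 over 48 weeks. To count as pre-specified under SAP section 4, the change must be logged in Appendix 4 before the statistician examines the data.

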## 6. STUDY METHODS

### 6.1. Overall Study Design and Plan

#### 6.1.1. Criterion for an Adaptive Change in Design

This multicenter, open-label, single-arm, adaptive, interventional study potentially has two parts with Part B contingent upon the outcome of Part A. *Whether or not Part B is to be invoked will be decided as follows.* When approximately 16 subjects enrolled in the study reach Month 6, the stimulation data from these subjects will be evaluated to determine if LH concentration at 30 minutes after GnRHa stimulation is suppressed to  $< 4$  mIU/mL.

1) If  $\geq 85\%$  of these first subjects are suppressed at 6 months then Part B will *not* be invoked and all subjects will be seen through the final planned Part A visit (i.e., Visit 8).

2) If approximately  $< 85\%$  of subjects ( $N \geq 3$ ) exhibit suppression the study will immediately proceed to Part B. If Part B is invoked subjects currently enrolled in Part A and have not yet received a 2nd injection, will be entered into Part B on Visit 7. Then, all future subjects enrolled in the study will undergo the equivalent of Visits 1 through 6 of Part A followed by Part B beginning on Visit 7.

#### 6.1.2. Design and Procedures for Part A and Part B

Subjects enrolled in Part A will receive their first injection on Visit 1 (Day 0). Part A will continue over 12 months with Visits 2, 3, 4, 5, 6, 7 and 8 respectively planned at Months 1, 3, 5, 6, 9, 11 and 12. Part B *if invoked* is planned over an additional 10 months and will begin at Visit 7 of Part A and continue through Visits 8, 9, 10 and 11 which shall correspond to Months 15, 16, 20 and 21.

Whether or not Part B is invoked, all subjects under Part A will receive a first treatment injection at Visit 1 (Day 0); and a second injection at Visit 5 (Month 6). If Part B is invoked then all subjects additionally will experience treatment injections on Visit 7 (Month 11) and Visit 9 (Month 16) under Part B. If only Part A is completed, the percent of subjects with suppression at 30 minutes after GnRHa stimulation of  $< 4$  mIU/mL at six (6) months will constitute the primary outcome variable. If part B is invoked, the primary outcome variable will be the percent of subjects with suppression at twenty-one (21) months.

The planned visits and data to be collected under Part A and under Part B (if invoked) are presented in the schematics that follow.

Table 1 Schedule of Assessments—Part A

Part A	Screening	Injection #1					Injection #2				End of Treatment 	Unscheduled Visit (PI discretion)
Visit Number:		Visit 1	Telephone Contact 1	Visit 2	Visit 3	Visit 4	Visit 5	Telephone Contact 2	Visit 6	Visit 7	Visit 8	
Scheduled Day/Week	Within 28 days	Baseline (Day 0)	Week 2 ± 2 days	Week 4 ± 7 days	Week 12 ± 7 days	Week 20 ± 7 days	Week 24 ± 7 days	Week 26 ± 2 days	Week 36 ± 7 days	Week 44 ± 7 days	Week 48 ± 7 days	
Scheduled Month (approximate)		--	~Month 0.5	~Month 1	~Month 3	~Month 5	~Month 6	~Month 6.5	~Month 9	~Month 11	~Month 12	
Written Informed Consent / Assent 	X											
Inclusion/Exclusion Criteria Review	X	X										
Demographics	X											
Medical History	X											
Complete Physical Examination	X										X	X
Query Subject: How have you felt in the last 2 weeks?			X	X	X	X	X	X	X	X	X	X
Directed Physical Examination		X		X	X		X		X			
Prior or Concomitant Medication Review / Medical Procedures	X	X		X	X	X	X		X	X	X	X
Tanner Stage	X				X		X				X	X
Vital Signs 	X	X		X	X	X	X		X	X	X	X
Weight	X	X		X	X	X	X		X	X	X	X
Height	X	X		X	X	X	X		X	X	X	X
Hand and Wrist X-ray	X						X				X	
Urine Pregnancy Test—females only		X					X				X	X
Urinalysis	X			X			X				X	X
Hematology	X			X			X				X	X
Chemistry	X			X			X				X	X

 If a decision is made to continue into Part B, neither Part A Visit 7 nor the End of Treatment assessment will be completed and subjects will proceed directly to the start of Part B Visit 7 of the study. See the following Schedule of Assessment for Part B.

 Informed Consent/Assent may be signed within 28 days prior to the Baseline visit.

 Vital signs are to be measured BEFORE any blood draws.

Part A	Screening	Injection #1					Injection #2				End of Treatment 	Unscheduled Visit (PI discretion)
Visit Number:		Visit 1	Telephone Contact 1	Visit 2	Visit 3	Visit 4	Visit 5	Telephone Contact 2	Visit 6	Visit 7	Visit 8	
Scheduled Day/Week	Within 28 days	Baseline (Day 0)	Week 2 ± 2 days	Week 4 ± 7 days	Week 12 ± 7 days	Week 20 ± 7 days	Week 24 ± 7 days	Week 26 ± 2 days	Week 36 ± 7 days	Week 44 ± 7 days	Week 48 ± 7 days	
Scheduled Month (approximate)		--	~Month 0.5	~Month 1	~Month 3	~Month 5	~Month 6	~Month 6.5	~Month 9	~Month 11	~Month 12	
Hepatitis B antigen/Hepatitis C antibody	X											
Serum lipids – fasting	X	X										

Table 1 Schedule of Assessments—Part A (continued)

Part A	Screening	Injection #1					Injection #2				End of Treatment 	Unscheduled Visit (PI discretion)
Visit Number:		Visit 1	Telephone Contact 1	Visit 2	Visit 3	Visit 4	Visit 5	Telephone Contact 2	Visit 6	Visit 7	Visit 8	
Scheduled Day/Week	Within 28 days	Baseline (Day 0)	Week 2 ± 2 days	Week 4 ± 7 days	Week 12 ± 7 days	Week 20 ± 7 days	Week 24 ± 7 days	Week 26 ± 2 days	Week 36 ± 7 days	Week 44 ± 7 days	Week 48 ± 7 days	
Scheduled Month (approximate)		--	~Month 0.5	~Month 1	~Month 3	~Month 5	~Month 6	~Month 6.5	~Month 9	~Month 11	~Month 12	
LH and FSH samples (basal)	X	See Table 2		X	X	X	X		X	X	X	X
Testosterone/estradiol samples (basal)	X	See Table 2		X	X	X	X		X	X	X	X
Serum Leuprolide samples (basal) 	X	See Table 2		X	X	X	X		X	X	X	X
GnRH a Stimulation (SC leuprolide acetate) 	X				X		X		X		X	X

 If a decision is made to continue into Part B, neither Part A Visit 7 nor the End of Treatment assessment will be completed and subjects will proceed directly to the start of Part B Visit 7 of the study. See the following Schedule of Assessment for Part B.

 Blood samples for leuprolide serum concentrations must be collected BEFORE the GnRHa stimulation test.

 GnRHa (SC) stimulation must be performed AFTER a blood sample has been collected for measurement of basal LH, FSH AND testosterone/estradiol concentrations and prior to study drug injection. Blood samples for LH, FSH and testosterone/estradiol concentrations must be obtained again 30 ± 5 minutes after SC administration of GnRHa. See Section 8.1.14.

Part A	Screening	Injection #1					Injection #2				End of Treatment 	Unscheduled Visit (PI discretion)
Visit Number:		Visit 1	Telephone Contact 1	Visit 2	Visit 3	Visit 4	Visit 5	Telephone Contact 2	Visit 6	Visit 7	Visit 8	
Scheduled Day/Week	Within 28 days	Baseline (Day 0)	Week 2 ± 2 days	Week 4 ± 7 days	Week 12 ± 7 days	Week 20 ± 7 days	Week 24 ± 7 days	Week 26 ± 2 days	Week 36 ± 7 days	Week 44 ± 7 days	Week 48 ± 7 days	
Scheduled Month (approximate)		--	~Month 0.5	~Month 1	~Month 3	~Month 5	~Month 6	~Month 6.5	~Month 9	~Month 11	~Month 12	
LH and FSH samples 30 ± 5 min AFTER GnRH a stimulation	X				X		X		X		X	X
Testosterone/estradiol samples 30 ± 5 min AFTER GnRH a stimulation	X				X		X		X		X	X
Study drug (leuprolide acetate) SC injection 		X					X					
Adverse Events Assessment		X		X	X	X	X		X	X	X	X
Schedule/Confirm Next Visit	X	X		X	X	X	X		X	X		(X)

 Local or topical anesthetic may be used at the discretion of the Investigator, prior to study drug administration. Name of the anesthetic used, route, and time of dose must be recorded.

Table 2 Blood Sampling Times by Parameter for Visit 1—Part A

Visit Number—Part A	Visit 1			
Scheduled Day/Month	Baseline (Day 0)			
	Time relative to injection			
	≥30 min prior	1 h (±5 min)	4 h (±10 min)	6 h (± 15 min)
LH and FSH samples	X	X	X	X
Testosterone/estradiol samples	X	X	X	X
Serum Leuprolide	X	X	X	X

Vital signs to be measured BEFORE any blood draws.

Table 3 Schedule of Assessments—Part B

Part B	Injection #3			Injection #4			End of Treatment	Unscheduled Visit (PI discretion)
Visit Number:	Visit 7	Telephone Contact 3	Visit 8	Visit 9	Telephone Contact 4	Visit 10	Visit 11	
Scheduled Day/Week	Week 44 ± 7 days	Week 46 ±2 days	Week 60 ± 7 days	Week 64 ± 7 days	Week 66 ±2 days	Week 76 ± 7 days	Week 80 ± 7 days	
Scheduled Month (approximate)	~Month 11	~Month 11.5	~Month 15	~Month 16	~Month 16.5	~Month 20	~Month 21	
Written Informed Consent / Assent 	X							
Complete Physical Examination							X	X
Query Subject: How have you felt in last 2 weeks?	X	X	X	X	X	X	X	X
Directed Physical Examination	X		X	X		X		
Prior or Concomitant Medication Review / Medical Procedures	X		X	X		X	X	X
Tanner Stage	X		X	X		X	X	X
Vital Signs 	X		X	X		X	X	X
Weight	X		X	X		X	X	X
Height	X		X	X		X	X	X
Hand and Wrist X-ray	X			X			X	
Urine Pregnancy Test	X			X			X	X
Urinalysis	X			X			X	X
Hematology	X			X			X	X
Chemistry	X			X			X	X
Serum lipids - fasting	X							
LH and FSH (basal)	X		X	X		X	X	X
Testosterone/Estradiol (basal)	X		X	X		X	X	X
Serum Leuprolide (basal) 	X		X	X		X	X	X
GnRHa Stimulation (SC leuprolide acetate)	X			X			X	X
LH and FSH samples 30 min AFTER GnRHa stimulation	X			X			X	X
Testosterone/estradiol samples 30 min AFTER GnRHa stimulation	X			X			X	X
Study drug (leuprolide acetate) SC injection 	X			X				
Adverse Events Assessment	X		X	X		X	X	X
Schedule/Confirm Next Visit	X		X	X		X		(X)

 Prior to start of Part B extension, parents/guardian(s) and subjects will be asked to sign a new ICF and assent, respectively.

 Vital signs to be measured BEFORE any blood draws

 Blood samples for leuprolide serum concentrations must be collected BEFORE the GnRHa stimulation on days the stimulation test is given.

 Local or topical anesthetic may be used at the discretion of the Investigator prior to study drug administration. Name of the anesthetic used, route, and time of dose must be recorded.

